2.1. Introduction

This chapter reviews what is expected from staff working on this research study. There will be a number of activities and tasks that staff will be expected to perform. Each of these roles include specific tasks and responsibilities that must be completed to a high standard. This chapter will describe the core activities and functions of each role.

All staff, regardless of level, are expected to represent a project that cares about people by always acting as role models and be kind to participants, other patients and healthcare staff. We encourage staff to show respect and be professional at all times while working on this study. Please note, we are guests in the healthcare facilities, therefore, it is critically important that we keep good relationships with all staff we engage with at the healthcare facility.

2.2. Roles and Responsibilities of Staff

2.2.1 Organogram

2.2.2 Project Staffing

There are a variety of staff working on this project.

Project Coordinator: is responsible for assisting the Site-PI with all study related activities and co-ordination, including applications for approval to the Department of Health. They are responsible for overseeing day-to-day activities, ensuring that all study-related materials and incentives are available. They are responsible for data management and will provide support in the reproduction of study-related materials, and assist with literature searches, preparation of slides and other materials for reports, presentations, and publications. They are supervising all field workers, provide training to field workers on recruitment, data collection and tracking procedures. They will conduct quality checking to ensure all data storage SOPs and data collection SOPs are being adhered to. This will include collection of self-report and biological data. They will be responsible for maintaining regulatory (GCP and ethics) oversight, maintenance and stock control of supplies.

Fieldworkers

Will be based at the participating healthcare facilities and MOUs. They will be responsible for conducting screening to identify potential patients who are eligible to participate in the study, consenting eligible patients and enrolling them in the study, scheduling appointments, collecting contact information, conducting the baseline and follow up assessments and tracking participants for study appointments. All of these activities will require the completion of certain paperwork that will be explained in subsequent chapters of this manual. When conducting such activities, staff members must be very conscientious about checking the quality of their own work and ensuring that all interviews are completely and accurately documented using the appropriate forms. Fieldworkers will report directly to the Project Coordinator and indirectly to the Site PI.

Fieldworkers Daily Tasks:

- Maintain confidentiality at all times,
- Be flexible with scheduling appointments (e.g., late afternoon appointments or weekend follow up appointments for assessments),
- Check the quality of own work,
- Check email accounts at least once daily,
- Check project-device messages regularly throughout the day,
- Maintain appointment book
- Keep all supplies in a secure location,
- Report any missing items immediately to the Project Coordinator and
- Report all incidents to the Project Coordinator as described in the ‘Incident Reporting’ chapter.

2.3. Staffing Operations

2.3.1 Staff Dress-code

All frontline staff for this study (including fieldworkers employed by the study) are expected to wear their MaRISA t-shirts when conducting research activities at the field site office, the healthcare facility and the communities. These t-shirts will be issued to staff. These t-shirts can preferably be worn with a pair of jeans or black pants and comfortable shoes. We expect all fieldworkers employed by the study to always look neat and professional.

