2.5.2 Health Facility Sites

At each health facility there will be a security company contracted to ensure the safety of all employees and patients, as well as keeping the building including all the assets on the premises intact. Employees are encouraged to familiarize themselves with the security personnel at the facility and establish their role at the facility. Employees should also enquire from the facility manager or operational manager at the facility what safety protocols the facility has in place so that they are aware of these protocols.

If you are concerned about a participant's mental status prior to commencing a scheduled appointment discreetly communicate the matter with the Project Coordinator, to discuss whether the participant needs to be rescheduled for another day and/or referred to the Emergency Room or Mental Health Nurse on duty.

When conducting case management activities, the following steps should be followed to ensure safety and security of assets:

- 1) First contact the participant telephonically a day before making a home visit.
- 2) During this call make an appointment with the participant for a specific day and time that you will be visiting them at their home, to ensure that they will be available.
- 3) **Please note: NO FIELDWORKER SHOULD CONDUCT CASE MANAGEMENT / HOME VISITS ALONE – ALWAYS BE ACCOMPANIED BY ANOTHER STAFF MEMBER.**
- 4) If at any time you feel uncomfortable, unsafe or threatened, communicate this with your companion and return to the health facility immediately. If this occurs prior to reaching the participant's home, then contact the participant when back at the health facility and explain the situation and try to reschedule another convenient time you can do a home visit.

- 5) Except for the study cell phone don't carry any other valuables with you when conducting home visits.

****Please remember to report any incident in your incident report form, which must be filled in immediately or soon after the incident, sent to the Project Coordinator and Site PI via email/electronically, and kept on file at the field site (Delft Office).**

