2.1. Ensuring Participants' Rights, Privacy, and Confidentiality

3.1.1 Participants' Rights

Basic human rights must be respected and maintained by a research organization and all who are involved in its activities. The protection of rights and confidentiality has always been especially critical in studies focused on substance use, where exposure of past or current abuse or addiction can have social, economic, and legal consequences. MaRISA's research procedures are designed to protect individual rights and to comply with all applicable laws and ethical principles. Among the rights that must be protected are:

- *The right to accurate representation:*
 - Requires honesty in dealing with participants and provision of completely accurate information about the study.
- *The right of informed consent:*
 - Requires that a participant be given adequate information to make an informed decision about participation.
- *The right to refuse:*
 - Requires that an individual be fully informed of his/her right to decline to participate, to withdraw, or to refuse to answer any question.
- *The right of privacy:*
 - Requires guarantees against invasion of privacy as well as specific protection as specified in the South African Protection of Personal Information Act of 2013.

These rights are extremely important to us as individuals and as professionals engaged in applied research. All SAMRC studies must develop specific written plans for conducting research with human subjects. Research staff must also operate under the supervision of committees for the protection of human subjects to ensure that they do not violate these rights.

In research involving follow-ups and contacts, it is necessary to collect names, addresses, and other personal information from participants for future follow-ups. A great deal of information collected from participants pose a risk to participants, especially if their use of substances is not known to others. It is extremely important that the data collected be kept confidential.

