5.2. Screening

Once introductions are made and a patient's cooperation has been secured, complete the participant ID, staff ID, site and date fields on the screener, using the tablet.

- For the pilot phase, we will be using the "Pilot Screener for Pregnant and Post-Partum Women" at the onset of the pilot phase.

Recruitment will be done via clinic referrals, posters, and flyers.

Participant IDs will be according to the following format, it will consist of ten digits with both alphabetic and numerical items, e.g., M_BL0001PR or M_BL0001PP.

Please note: the first alphabetic digit refers to the MaRISA study, an underscore sign separates it from the next 2 alphabetic digits which indicates the site, e.g., Bishop Lavis = M_BL, the next 4 digits indicates how many participants have been enrolled into the study and the last 2 digits indicates whether the participant is currently pregnant or post-partum.

There are types of potentially sensitive information that are requested on the screening questionnaire. It is important to stress the confidential nature of the screener. Reassure them that their identity will never be linked to their responses and that their responses are only used for research purposes. Always remind individuals that their answers will be kept strictly confidential.

Staff ID#: Will be a staff member's Initials.

Site ID#: Bishop Lavis = M_BL; Macassar = 002

To be eligible, women must fulfil in the following criteria, i.e.:

Criterion	Participants
Age	Be ≥ 18
Pregnancy or Post-Partum Status	be pregnant (≤ 28 ges wks) or postpartum (≤ 3 mos)
Alcohol Use	
 have reported alcohol use during the current pregnancy or lactation test positive for alcohol use by urinalysis (i.e., EtG)
Birth Venue (linked to birth outcomes)	plan to complete antenatal care at the current clinic and remain in the area for at least 3 months
Cellphone Status	own a cell phone to receive text messages
Serious Medical Conditions and Suicidal Thoughts	women who report serious medical problems threatening their current pregnancy or report current suicidal thoughts or attempts in the past month are NOT eligible
Other	intend to breastfeed for 6 months

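### The dress code puts study-branded shirts on staff in the communities, and with no exception for home visits in the supplied text this can disclose a visited woman's participation, and so her alcohol use.

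*Protocol*

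**What the plan says.** **Dress code.** Protocol 2.3.1 applies to all frontline staff and names fieldworkers expressly. They "are expected to wear their MaRISA t-shirts when conducting research activities at the field site office, the healthcare facility and the communities". The section gives no exceptions.

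**Home visits.** Protocol 2.5.2 lists five steps for case management visits. The fieldworker phones beforehand: "First contact the participant telephonically a day before making a home visit". The call fixes the visit: "During this call make an appointment with the participant for a specific day and time that you will be visiting them at their home". Staff go in pairs: "NO FIELDWORKER SHOULD CONDUCT CASE MANAGEMENT / HOME VISITS ALONE". The other steps deal with leaving if unsafe and not carrying valuables. None deals with clothing, or with how staff identify themselves to other people at the house.

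**Who can be a participant.** The introduction to Chapter 5 requires both pregnant and postpartum women to report alcohol use. The eligibility table in 5.2 adds a positive urine EtG test, and the dispositions table lists both a negative EtG and no alcohol use as reasons for not taking part.

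**Visibility of the study.** The SAP heading expands the acronym to Maternal Alcohol Reduction Intervention in South Africa. Protocol 5.2 states: "Recruitment will be done via clinic referrals, posters, and flyers".

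**Confidentiality.** Protocol 3.1.1 warns that much of the information collected can "pose a risk to participants, especially if their use of substances is not known to others". Protocol 3.5.1 tells staff to refuse family members any information on a participant. It accepts that clinic staff may know who is in the study, and it makes no such allowance for family or neighbours.

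**The concern.** In most studies, knowing that someone takes part reveals little. Here enrolment depends on alcohol use in the current pregnancy or lactation, so participation itself is sensitive information. A rule that sends staff to a participant's home in clothing carrying the study name can reveal that information while everyone follows the manual.

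What is at stake is the woman's safety and privacy. The Chapter 7 introduction lists social ramifications of taking part among the risks. Section 7.1 gives, as an example of a reportable incident, a husband's abuse of a woman because she is in the study. The event table in Chapter 7 includes physical violence resulting from participation. Those passages govern reporting after harm has occurred. The dress code is a point at which one possible route to that harm can be closed beforehand.

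**Working it through.** No calculation applies: the point depends on no error rate, effect size or sample size. The check is whether each link in the chain is in the text.

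1. **Does the shirt rule reach home visits?** The dress code covers research activities in the communities but does not name home visits. Section 2.5.2 describes fieldworkers visiting participants at home. It calls this case management, but section 2.2.2 gives fieldworkers the study duties of "conducting the baseline and follow up assessments and tracking participants for study appointments", and home visits serve that tracking. The Chapter 7 event table also refers to household visits in its examples. Screening is set in the healthcare facilities, and 5.4 places the follow-up assessments there. Home visits are thus the main participant contact in the community that the manual describes. Read together, 2.3.1 and 2.5.2 cover them.

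2. **Is there an exception?** None appears in 2.3.1 or in the five steps of 2.5.2.

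3. **Does participation imply alcohol use?** Yes. Reported use and a positive EtG are both conditions of enrolment, and failing either is a listed reason for exclusion. There is no non-drinking group of participants that would make enrolment ambiguous.

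4. **Can an onlooker make the connection?** Only one who knows what MaRISA is and takes the visited woman to be enrolled. Posters and flyers make such knowledge plausible, but the documents do not give their content or where they are displayed. This link is possible and not established.

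5. **Does this conflict with the manual's own rules?** Section 3.5.1 bars telling relatives anything about a participant, and 3.1.1 identifies women whose use is hidden as those at greater risk. A branded shirt at the door can convey to relatives or neighbours what staff may not say.

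6. **How many women?** The introduction to Chapter 5 plans 60 women (30 pregnant and 30 postpartum). No number or frequency of home visits is given, so the number visited could lie anywhere from 0 to 60.

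**The case against.** The strongest reply is that exposure may be rare and is partly under the woman's control. Fieldworkers are based at the facilities. Section 2.6 pays transport for urine monitoring there. The missed-visit procedure in 5.4 consists of phone calls on the appointment day, the next day and one week later, with no home visit listed. Section 2.5.2 says how to make a home visit but not when one is needed, and the call the day before lets the woman choose the time or decline. Confidentiality is also a standing daily duty in 2.2.2. All of this stands and limits the likely size. It does not answer the point, because nothing says she is told that the visitors will wear study shirts, and neither the call nor the general duty removes the shirt.

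A reader might infer that the shirt marks the visited woman as a drinker with certainty. The documents do not support that. They do not say what is printed on the shirt beyond calling it a MaRISA shirt, and in the text available the full name containing the word alcohol appears only in the SAP heading. The certain step is from participant to alcohol use. The step from shirt to participant depends on what the onlooker knows.

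A reader might also infer that the shirts bias the results by driving away women who hide their drinking. Nothing in the documents links shirts to refusal or dropout. The SAP plans descriptive summaries and a trend test, and no estimate is shown to change.

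Finally, the consent pages and a short part of the manual just before section 2.5 were not in the text available for this check, and the contact and locator forms are named but not shown. An exception there, or a question about how staff should identify themselves, cannot be ruled out.

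**Conclusion.** The point holds as a participant-protection matter. As written, the dress code read with the home-visit steps has staff wearing study-branded clothing at participants' homes. To people who know the study, that can disclose participation and so alcohol use in pregnancy or lactation. This is at odds with 3.1.1 and 3.5.1, and it could contribute to harms that Chapter 7 recognises.

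The conclusion rests on three assumptions: that home visits count as research activities in the communities, that the shirt shows the study name, and that no exception exists in the material not supplied. The number of home visits and any effect on retention are unknown. The point does not invalidate the study or alter any planned analysis. It is worth acting on because the risk is foreseeable, arises from a stated rule, and is cheap to remove.

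**What to change.** Amend 2.3.1 so that, on home visits and any other contact in the community directed at a particular participant, staff wear no clothing bearing the study name. They use plain clothes or a neutral institutional shirt and carry a staff identity card. Add a cross-reference to this rule among the home-visit steps in 2.5.2. Branded shirts at the field office and the healthcare facility may stay, since the argument concerns only contact in the community.

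The cost is one sentence, one cross-reference and neutral shirts for a few fieldworkers. Staff are slightly less identifiable with this particular study in the community, but the identity card still shows who they are. No endpoint, assessment or analysis changes.

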2.5 Safety Procedures at Project Sites

2.5.1 Delft Offices (Field Site)

In order to encourage the safety of staff and all assets situated at the Delft office we would like to promote the following safety measures to be taken on a daily basis:

- Always ensure that the project site gates are kept locked.
- Never allow anyone who looks suspicious to enter the site, rather talk to them through the security gate.

- No expensive assets such as devices, computers, cameras, cell phones etc. should be left out overnight; please make sure that all assets are locked-up before leaving at the end of day.
- Also ensure that all windows are closed, and air conditioners are switched off before leaving at the end of day.

2.5.2 Health Facility Sites

At each health facility there will be a security company contracted to ensure the safety of all employees and patients, as well as keeping the building including all the assets on the premises intact. Employees are encouraged to familiarize themselves with the security personnel at the facility and establish their role at the facility. Employees should also enquire from the facility manager or operational manager at the facility what safety protocols the facility has in place so that they are aware of these protocols.

If you are concerned about a participant's mental status prior to commencing a scheduled appointment discreetly communicate the matter with the Project Coordinator, to discuss whether the participant needs to be rescheduled for another day and/or referred to the Emergency Room or Mental Health Nurse on duty.

When conducting case management activities, the following steps should be followed to ensure safety and security of assets:

- 1) First contact the participant telephonically a day before making a home visit.
- 2) During this call make an appointment with the participant for a specific day and time that you will be visiting them at their home, to ensure that they will be available.
- 3) **Please note: NO FIELDWORKER SHOULD CONDUCT CASE MANAGEMENT / HOME VISITS ALONE – ALWAYS BE ACCOMPANIED BY ANOTHER STAFF MEMBER.**
- 4) If at any time you feel uncomfortable, unsafe or threatened, communicate this with your companion and return to the health facility immediately. If this occurs prior to reaching the participant's home, then contact the participant when back at the health facility and explain the situation and try to reschedule another convenient time you can do a home visit.

- 5) Except for the study cell phone don't carry any other valuables with you when conducting home visits.

****Please remember to report any incident in your incident report form, which must be filled in immediately or soon after the incident, sent to the Project Coordinator and Site PI via email/electronically, and kept on file at the field site (Delft Office).**

2.5.3 Engaging with Health Facilities

After receiving an approval letter from the Department of Health indicating that you can continue with all research activities at a facility, communication should follow in a systematic manner.

- **Step 1** - Contact senior management (Facility Manager (FM), Operational Managers (OPMs) & Fam. Physician) via email to introduce the study, provide them with the approval letter and schedule an appointment for research purposes / a visit.
- **Step 2** - Always follow-up a day or two later telephonically if you didn't receive response via email; if you have received response the telephonic follow-up should still occur to confirm details of appointment.
- **Step 3** - Prior to going to the facility follow-up a day before, telephonically or via email to remind management that you will be coming to the facility to conduct research activities / a visit etc.
- **Step 4** - On the day of the appointment (depending on the visit), on arrival at the facility always first go to the FM or OPM to greet them and inform them that you are at the facility for the day and also provide them again with a hard-copy of the approval letter if it's the first day or first time you come to the facility.

2.6 Protocol for Petty Cash

The SAMRC will advance petty cash to the Project Coordinator, amounts of which will be determined by the needs of the project. Requests for petty cash must be submitted to the SAMRC through the JDE financial system at least one month in advance to ensure money will be available to reimburse participant's transport fees.

Prior to the initiation of recruitment procedures, each field worker will be issued a specific calculated amount by the Project Coordinator to reimburse participant's transport fees. The fieldworker will sign a receipt documenting they acknowledge receipt of the money and that they will be held responsible if the participant does not receive their reimbursement. It will also be the fieldworker's responsibility to make sure the participant signs the receipt book when issued with the transport fee. Transport fee will be issued only at study required appointments, i.e. when participants need to visit the healthcare facility for urine monitoring or if the baseline appointment is scheduled on a different day than the screening appointment. The petty cash received needs to be locked up in a lockable petty cash box, which will be kept in a double lockable steel cabinet, and only the fieldworker and Project Coordinator should have access in the form of keys to both the petty cash box and the cabinet. **Under no circumstances should the petty cash box be left out unlocked and unattended during the day or be left out overnight.**

